7.9. Long term follow-up assessments

Nil

7.10. Quality of life assessments

KCCQ: a 23-item questionnaire measuring symptoms, physical and social limitations, and QoL in patients with heart failure. Scores range from 0-100 with lower scores representing worse quality of life.

DTSQ Status and Change: Assesses patient-reported outcomes related to their diabetes treatment. Includes eight items, and responses are scored on a 7-point scale, from +6 to 0. The scores of six items (satisfaction with current treatment, convenience, flexibility, understanding of diabetes, recommend treatment to others and willingness to continue) are added together to give the overall treatment satisfaction score (range +36–0), with higher scores denoting greater treatment satisfaction. The perceived frequencies of hyperglycaemia and hypoglycaemia are also assessed, rated on a scale of +6 (“Most of the time”) to 0 (“None of the time”). The DTSQ status version will be used at baseline and 16 weeks, while the DTSQ change version will also be performed at 16 weeks. This is a focused version of the questionnaire designed to overcome potential ceiling effects where respondents score near-maximum satisfaction at baseline and therefore have little room for improvement at follow-up.

EQ-5D-5L: A generic measure of QoL that can be used for multiple patient groups across different conditions. Patients will perform the EQ-5D-5L at baseline and 16 weeks.

7.11. Withdrawal criteria

Participants are free to withdraw at any time and are not obliged to give a reason(s). However, the CI, PI or delegate will make a reasonable effort to ascertain the reason(s), both for those who express their right to withdraw and for those lost to follow-up, while fully respecting the individual’s rights.

The investigator may withdraw a participant at any time if it is in the best interest of the participant and treatment continuation would be detrimental to the participant’s wellbeing. The Investigator will make a clinical judgment as to whether an AE is of sufficient severity to require

the participant's removal from treatment. A participant may also voluntarily withdraw from treatment due to what he or she perceives as an intolerable AE. If either of these occurs, the participant should, if required, be offered an end-of-trial assessment.

A full explanation will be provided. As the trial is being conducted on an intention to treat basis, if the participant has been randomised and given one or more doses of IMP, s/he will be asked to complete trial visits as per the protocol, to allow for an intention to treat analysis – but will be censored in the per-protocol analysis. Participants are free to refuse to do so. Withdrawn participants will not be prescribed IMP.

Those withdrawn, including those lost to follow-up, will be identified and a descriptive analysis of them provided, including the reasons for their loss, if known, and its relationship to treatment and outcome.

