Once randomisation is complete, individuals with an HbA1c <58mmol/mol at screening will have a 10% insulin dose reduction prior to taking their first dose of sotagliflozin/placebo. No reduction in insulin dose will be made for those with HbA1c ≥58mmol/mol at screening. All participants will then be advised to monitor regularly and to adjust insulin doses every 24-48 hours to achieve recommend blood glucose targets.

The total, basal and bolus doses of insulin used will be recorded for analysis for the 7 days prior to the trial visits at randomisation, week 4 and week 16.

Blood glucose management:

All participants will use CGMs that are supplied in the UK as standard care and data from these will be assessed at each visit by the local investigator or delegate. Participants who do not wish to use CGM will not be eligible to participate in the trial.

Where participants have a compatible CGM they will be asked if they wish to sign-up to free to use apps such as LibreView (Abbott) or Clarity (Dexcom). Participants create their own account and can download their blood glucose readings then give access to local investigators to view reports to assist with glucose management. Consent will be sought to share summary data from these reports and/or CGM recordings with the trial investigators. Participants who do not wish to sign-up to one of these apps will not be excluded from participating in the trial.

Investigators will recommend alarm settings on participants CGM to be set at a high alarm of 15 mmol/L (13 mmol/L if on an insulin pump) and a low alarm of 3.9 mmol/L. The lower alarm may be subsequently adjusted based on clinician and participant judgment and preferences. Alarm levels and CGM metrics should be assessed by the local research team at each visit.

CGM data will be entered into the data management system for trial analysis for the 2 weeks prior to the trial visits at randomisation, week 4 and week 16. Where available LibreView/Clarity etc. summary data will be used. The variables collected will include:

- Number of days CGM worn
- Percentage of time CGM is active
- Mean glucose
- Glycaemic variability (%CV).
- Percentage time in target, time above target and time below target.

Diabetic ketoacidosis (DKA):

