7.11.1. Discontinuation of trial drug

The trial drug will be discontinued permanently in the following circumstances:

- Recurrent (more than 2) level 3 hypoglycaemia events with no other contributing factors, e.g. diet or exercise.
- DKA requiring hospitalisation.
- Renal failure requiring dialysis.
- Pregnancy.
- Diagnosed Fournier's gangrene.
- Circumstances where the PI feels that continuation of trial drug will be detrimental to the participant's well-being.

Where the participant, for whatever reason, permanently discontinues the trial drug they will be encouraged to remain in the trial completing all follow-up visits and calls.

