10.3.1. Primary outcome analysis

The primary endpoint of change in KCCQ clinical summary score at 16 weeks will be analysed using mixed effect models adjusting for baseline KCCQ, age, eGFR and LVEF.

Statistical significance will be defined as a two-sided p value <0.05 for all tests.

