10.5. Participant population

The primary analysis will be by intention to treat (ITT), defined as all participants successfully randomised. Sensitivity analyses using both modified ITT (all randomised participants with at least one evaluable endpoint) and per-protocol data will also be performed.

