	Research Site	Remote/ Research Site	Research Site	Remote/ Research Site	Research Site	Remote/ Research Site	Research Site	Remote/ Research Site
Sub-study***								
CMR scan		X					X	
Height and Weight		X					X	
FBC		X					X	
Heart rate and blood pressure		X					X	

*The timing of the echocardiogram can vary as long as results are available in time for confirmation of participant eligibility at visit 3.

Dispensing may be delayed by up to 3 days to facilitate local practices. *CMR sub-study assessments may not necessarily be performed on the same day as the rest of the visit due to scheduling, some variation in the timing of the scan is acceptable. CMR will be performed within the following timescales:

- Baseline CMR scan: Day -30 to day 0.
- Visit 7 (week 16) – End of treatment scan. This can be performed up to 7 days prior to and 7 days after the scheduled visit 7.

[figure not shown]

Figure 1. Timing of CMR in relation to the main trial visits.

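### Section 7.11 asks only dosed participants to complete visits after withdrawal, although it serves an ITT analysis that section 10.5 defines as all randomised

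*Protocol*

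**What the plan says.** Section 7.11 (Withdrawal criteria) states that the trial is run on an ITT basis and derives its follow-up request from that: "if the participant has been randomised and given one or more doses of IMP, s/he will be asked to complete trial visits". The stated purpose is "to allow for an intention to treat analysis". The same section says that participants may refuse, and that those who withdraw will be identified and described.

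Section 10.5 (Participant population) fixes the analysis sets: "The primary analysis will be by intention to treat (ITT), defined as all participants successfully randomised". The sensitivity set, "modified ITT (all randomised participants with at least one evaluable endpoint"), has no dosing condition either.

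Section 7.11.1 (Discontinuation of trial drug) adds that a participant who "permanently discontinues the trial drug they will be encouraged to remain in the trial completing all follow-up visits and calls".

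On timing, Appendix 4 places randomisation and dispensing at Visit 3, with the note "Dispensing may be delayed by up to 3 days to facilitate local practices". Under Insulin Management in section 7.8, participants with a screening HbA1c below 58 mmol/mol "will have a 10% insulin dose reduction prior to taking their first dose of sotagliflozin/placebo", and this step comes after randomisation.

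**The concern.** The request in 7.11 is justified by ITT but carries a condition that ITT, as defined in 10.5, does not have. Data collection after withdrawal is therefore specified for a treated population, while the primary analysis is specified for all randomised.

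The people affected are those who withdraw between randomisation and the first dose. They count in the primary analysis set, but no passage asks them to return at week 16. That matters for the primary endpoint: "The primary endpoint of change in KCCQ clinical summary score at 16 weeks will be analysed using mixed effect models". It also matters for the DKA and hypoglycaemia proportions, which section 3.2 reports from week 0 to weeks 16 and 20.

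A statistical analysis plan can say how missing outcomes are handled. It cannot recover a questionnaire that the site was never told to request once the visit window has passed.

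**Working it through.** **Step 1: who is covered by which passage**

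| Participant after randomisation | Asked to complete visits? | In the ITT set (10.5)? |
|---|---|---|
| Dosed, then withdraws | Yes, 7.11 | Yes |
| Dosed, stops drug permanently | Encouraged, 7.11.1 | Yes |
| Never dosed, does not withdraw | Stays on the Appendix 4 schedule | Yes |
| Never dosed, withdraws | Not asked in 7.11; 7.11.1 is worded for people who stop a drug they had started | Yes |

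Only the last row shows a mismatch.

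**Step 2: can the last row occur?** Yes. Dispensing may lag randomisation by up to 3 days, some participants have an insulin reduction before the first dose, and 7.11 allows withdrawal at any time.

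**Step 3: reproduce the planned sample size.** Inputs from section 10.1: difference 4.7 points, SD 13.7, power 80%, alpha 0.05 (two-sided, section 10.3.1), allocation 1:1 (section 4).

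- n per arm = 2 × (1.960 + 0.842)² × 13.7² / 4.7² = 133.4, rounded up to 134, so 268 in total. This matches the protocol. An exact t-test calculation gives 135 per arm, with 79.9% power at 134.
- Inflation for 15% dropout: 268 / 0.85 = 315.3, rounded up to 316. The plan recruits 320.
- Evaluable at 320 with 15% dropout: 320 × 0.85 = 272, or 136 per arm.

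**Step 4: effect on power.** The protocol gives no never-dosed rate, so a share f is assumed. If those losses come on top of the 15%, evaluable N = 272 − 320f, and power = Φ(4.7 / (13.7 × √(2/n)) − 1.960), with n = N/2.

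| f (assumed) | Lost of 320 | Evaluable N | Power |
|---|---|---|---|
| 0% | 0 | 272 | 80.8% |
| 1% | 3.2 | 268.8 | 80.3% |
| 2% | 6.4 | 265.6 | 79.8% |
| 3% | 9.6 | 262.4 | 79.4% |
| 5% | 16 | 256 | 78.4% |

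If the never-dosed withdrawals are already part of the 15% allowance, evaluable N stays at 272 and power at 80.8%.

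**The case against.** The other side has a good deal to say, and most of it stands.

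- **A reader might infer that never-dosed participants lose their week-16 score by rule.** The text does not say so. Section 7.11 concerns people who withdraw. It does not forbid visits for the never-dosed, and a never-dosed participant who has not withdrawn keeps the full Appendix 4 schedule, including the KCCQ at weeks 4 and 16.
- **A reader might infer that the ITT analysis becomes an at-least-one-dose analysis.** Membership of the set does not change: 10.5 keeps every randomised participant. What may be missing is an outcome for a few of them, and section 10.3 assigns the handling of missing data to the statistical analysis plan.
- **A reader might infer bias.** If 3 to 10 people were lost from one arm of 160 and differed from the rest by 10 points, that arm's mean would shift by (3/160) × 10 = 0.19 to (10/160) × 10 = 0.63 points, against a target of 4.7. This stacks an assumed count, an assumed 10-point difference and a wholly one-sided loss. Participants and staff are blinded (section 7.4), those lost have taken nothing, and the insulin step depends on screening HbA1c and not on arm. Pre-dose withdrawal should therefore not depend on allocation. If both arms lose alike, their shifts cancel in the treatment difference.
- **Section 7.11.1 applies whatever the reason for stopping** and sets no minimum dose. It shows a general intent to keep people in follow-up, but its wording presupposes that the drug was started, so it does not clearly cover never-starters.
- **The dispensing delay is optional and short.** It makes the case possible; it does not show that it is common.

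None of this removes the mismatch between the condition in 7.11 and the definition in 10.5.

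**Conclusion.** There is a genuine but minor inconsistency. Section 7.11 limits its request to dosed participants while citing an ITT analysis that 10.5 defines without a dosing condition. The gap is confined to participants who withdraw after randomisation and before the first dose. They remain in the ITT set, but the protocol does not ask for their week-16 KCCQ or safety outcomes.

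The number affected is not stated and is probably small. At an assumed 1-3% (about 3 to 10 of 320), power falls by 0.5 to 1.4 percentage points from 80.8% if the losses are additional to the 15% dropout, and by nothing if they fall within it. No systematic bias between arms is expected, provided blinding holds. The stated 268 and 320 stand. The case for acting is that the correction is nearly free and an outcome not requested in time cannot be recovered.

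**What to change.** In section 7.11, delete the condition that at least one dose of IMP was given. The sentence should then say that any randomised participant who withdraws will be asked to complete the trial visits, whether or not any IMP was taken, with the existing right to refuse kept. State a minimum for those who will not attend in full: the week-16 KCCQ and safety events. Tell sites that this includes people who withdraw before dispensing or before the first tablet.

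The cost is a wording change, a line of site guidance and visits for what is likely to be a handful of people. The sample size, treatment and clinical rules are not affected.

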7.11.1. Discontinuation of trial drug

The trial drug will be discontinued permanently in the following circumstances:

- Recurrent (more than 2) level 3 hypoglycaemia events with no other contributing factors, e.g. diet or exercise.
- DKA requiring hospitalisation.
- Renal failure requiring dialysis.
- Pregnancy.
- Diagnosed Fournier's gangrene.
- Circumstances where the PI feels that continuation of trial drug will be detrimental to the participant's well-being.

Where the participant, for whatever reason, permanently discontinues the trial drug they will be encouraged to remain in the trial completing all follow-up visits and calls.

7.11.2. Temporary discontinuation of trial drug

The trial drug will be temporary discontinued in the following circumstances:

- Potential DKA: Participants will be instructed to stop their trial drug if blood ketones are >1.5mmol/L. Restarting of the trial drug is at the discretion of the local investigator, however it is anticipated that this will not be restarted until ketones are <0.6mmol/L and symptoms (if present) have resolved.
- Clinically significant volume depletion (as judged by the local investigator) or intercurrent illness may necessitate a temporary cessation of trial drug, although additional steps should be taken initially as appropriate such as increasing fluid intake, adjusting loop diuretic dose.
- Suspected Fournier's gangrene.
- If the patient has stopped trial drug for >5 consecutive days, the PI should be notified to confirm that it is appropriate to restart the trial drug on a case-by-case basis.

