Participants with type 1 diabetes should be aware of diabetic ketoacidosis. Further information on how to prevent, recognise, and treat DKA will be provided along with educational prompts. Participants will be also educated about precipitating factors for DKA (e.g. acute medical illness, vomiting, insulin pump failure, excessive carbohydrate restriction, excessive alcohol), when to discontinue therapy if these events occur and will be provided with contact details of the local research team and relevant emergency contacts for advice should any of these situations occur.

In addition to the above monitoring, participants will be advised to perform additional ketone testing if capillary/CGM glucose is >11.1 mmol/L for >2 hours or if feeling sick, according to standard sick day rules for diabetes management. Participants will be advised to check blood ketones if feeling unwell even when the capillary glucose levels are not particularly high, or with changes in diet, activity, insulin dose or events known to precipitate ketoacidosis and follow sick day rules as discussed with local team. If blood ketones are ≥ 0.6 mmol/L the clinician and participant will be encouraged to document reasons (e.g., alcohol, recent illness) for this and how it was managed. Advice will also be given regarding other times to check ketone levels (e.g., guidance is also given in Appendix 6 STOP-DKA protocol)⁴¹. Participants may be given a copy of the STOP-DKA guidelines, or local guidelines, dependent on local investigator's preference.

In summary the following strategies will be used to minimise DKA risk in addition to the educational measures:

- Participants will be asked to perform capillary ketone testing 4 times per day, 3 days before and 3 days after initiation of active drug/placebo, and 2 hours after changing each insulin giving set for those on insulin pump therapy as described earlier.
- Risk mitigation strategies, e.g. following the STOP-DKA Protocol if feeling sick or unwell with symptoms suggestive of impending DKA.

DKA will be defined as: blood ketone >3.0 mmol/l **and** blood pH of <7.3 or a bicarbonate <18 mmol/l.

Hypoglycaemia:

Hypoglycaemic events during the trial will be defined and documented as the following:

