16.1. Appendix 1 – Risk

Risks associated with trial interventions			
 A ≡ Comparable to the risk of standard medical care  B ≡ Somewhat higher than the risk of standard medical care  C ≡ Markedly higher than the risk of standard medical care			
Justification:			

As outlined in the table below and in the protocol, there are known risks with sotagliflozin in this group of patients (DKA, hypoglycaemia, volume depletion) that are greater than standard care. These are however known and the research team have introduced mitigations to manage these. This also is balanced against the likely benefit from SGLT2 inhibitors in patients with HF (and also in glycaemic control) that could lead to an improvement in clinical status. Overall the Sponsor therefore judges the risk to be somewhat higher than standard medical care.
			
What are the key risks related to therapeutic interventions you plan to monitor in this trial?		How will these risks be minimised?	
IMP	Body system/Hazard	Activity	Frequency
IMP	DKA	See section 7.8: Review of glucose management and DKA	At every visit
IMP	Hypoglycaemia	See section 7.8: Review of glucose management and DKA	At every visit
IMP	Genital/Urinary Tract Infections	Advice on risk of urogenital infection given at the randomisation visit as per standard initiation of SGLT2 inhibitors.	At randomisation
IMP	Fournier's Gangrene (necrotising fasciitis of the perineum)	Advice on risk of Fournier's Gangrene, the symptoms to watch for and the importance of seeking immediate medical attention if having these given at the randomisation visit as per standard initiation of SGLT2 inhibitors.	At randomisation and every visit afterwards

		Participants presenting with pain or tenderness, erythema, or swelling in the genital or perineal area, along with fever or malaise, should be assessed for necrotising fasciitis. If suspected, should discontinue trial drug and start treatment immediately with broad-spectrum antibiotics and, if necessary, surgical debridement.	
IMP	Volume Depletion	Advice given regarding “sick day rules” as per the STOP-DKA protocol (appendix 6).	At every visit
IMP	Blood creatinine increased/ Glomerular filtration decreased and renal-related events	Careful attention to fluid status and signs and symptoms of dehydration.	Renal function at visits 3, 5 and 7; renal-related events at every visit

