16.6. Appendix 6 – STOP-DKA Protocol

From Goldenberg et al. 2019⁴¹

The STOP-DKA protocol provides advice to clinicians that should be taken into consideration when starting sotagliflozin/placebo. This is simply provided for some general guidance that could be offered to participants but is not mandatory for use by sites. This is summarised in the figure below:

Initial recommendations when starting an SGLT inhibitor in an individual with type 1 diabetes

- Prescribers should have expertise in the management of type 1 diabetes
- Prescribers should use agents approved for use in type 1 diabetes
- Prescribe lower doses of SGLT inhibitors
- Adjust basal and bolus insulin based on SMBG and
 - Try to avoid insulin dose reduction of more than 20%
 - Never stop insulin
- Reassess insulin: carbohydrate ratios and insulin sensitivity factor once the patient is stabilized on the SGLT inhibitor
- Ensure patient gets a blood ketone monitor (urine ketone monitoring is not recommended)
- Provide patient with the **STOP DKA** protocol and wallet card as part of a risk mitigation strategy for DKA prevention

General principles for reducing ketosis and mitigating risk of diabetic ketoacidosis in symptomatic SGLT inhibitor-treated individuals with type 1 diabetes

- | | |
|---|--|

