| 
▪ Recognize the symptoms of DKA
▪ Nausea vomiting abdominal pain malaise worsening polyuria polydypsia shortness of breath▪ Avoid very low carbohydrate and ketogenic diets▪ Avoid excess alcohol▪ Exert caution with extreme exercise▪ Stop SGLT inhibitor at least 3 days prior to a major surgery▪ Never stop taking insulin | 
▪ Sick-day management
▪ Stop SGLT inhibitor▪ If symptomatic, check blood ketones and glucose▪ Consult the STOP DKA table for supplemental bolus insulin and carbohydrate recommendations even if blood glucose is normal▪ Keep hydrated during acute illness
▪ Ingest at least 250–500 mL of sugar-free and/or carbohydrate-containing fluids every 2–4 hours▪ Check insulin pump for potential delivery issue
▪ Inject insulin subcutaneously if necessary▪ Seek medical attention if
▪ high levels of ketones persist despite extra insulin and/or increased carbohydrate intake over a 6–10 hours period▪ vomiting▪ unable to keep down fluids▪ there are persistent symptoms of DKA |
|---|--|

A 2-sided wallet card is available, reproduced below. This could be provided to participants in the trial.

STOP-DKA Wallet Card

This card holder takes diabetes medication that can cause diabetic ketoacidosis without high glucose levels

STOP DKA Protocol

Symptomatic (e.g. lethargy, loss of appetite, nausea, abdominal pain) → STOP SGLT*i*

Test ketones* and glucose every 2-4 hours
(even if blood glucose is not elevated)

Oral ingestion of fluid and carbohydrates
(250–500 mL fluid every 2 hours and up to 30–60 g of carbohydrates every 2-4 hours)

Protocol instructions for supplemental insulin and carbohydrates
(see STOP DKA table)

*Ketosis/DKA may occur without an elevated blood glucose

STOP DKA Considerations for Bolus Insulin and Carbohydrates (for moderate or higher ketones, consider increasing basal insulin by 20%–50% until ketones return to normal)			
KETONE level (mmol/L) and category (check every 2–4 h)	BLOOD GLUCOSE* (check every 2–4 h)		
	4.0–8.0 mmol/L (70–150 mg/dL)	8.1–14.0 mmol/L (151–250 mg/dL)	>14 mmol/L (>250 mg/dL)

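### Section 7.11.2 puts fluids or a diuretic change ahead of pausing trial drug in acute illness, the reverse of the stop-first sick-day advice that the protocol cites elsewhere

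*Protocol*

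**What the plan says.** Section 7.11.2 lists the circumstances for a temporary stop of trial drug. The first bullet is a firm rule: participants stop if blood ketones exceed 1.5 mmol/L. The second bullet begins "Clinically significant volume depletion (as judged by the local investigator) or intercurrent illness may necessitate" and, from its mention of illness, reads on: "intercurrent illness may necessitate a temporary cessation of trial drug, although additional steps should be taken initially as appropriate". The steps it names are more fluid and loop diuretic adjustment.

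Four other places bear on the same participant:

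- **Section 2.1** says that volume depletion usually arises during an intercurrent illness, with diarrhoea or vomiting as examples.
- **Section 7.8** says that participants will be taught about "precipitating factors for DKA (e.g. acute medical illness, vomiting, insulin pump failure" and others. The same sentence says that they will be taught when to discontinue therapy if these events occur, and given contact details for advice. The section also names the STOP-DKA protocol as a risk strategy for participants who feel unwell with symptoms of impending DKA.
- **Appendix 1**, volume-depletion row, gives one mitigation, at every visit: advice on sick day rules "as per the STOP-DKA protocol (appendix 6").
- **Appendix 6** opens its sick-day list with "Stop SGLT inhibitor". The wallet card shown there goes from symptoms directly to stopping the drug, then to testing, then to fluids and carbohydrate.

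Appendix 6 also limits its own force: "This is simply provided for some general guidance that could be offered to participants but is not mandatory for use by sites". Section 7.8 adds that "Participants may be given a copy of the STOP-DKA guidelines, or local guidelines", at the local investigator's preference.

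**The concern.** The second bullet of 7.11.2 treats two clinical situations as one. Fluids and a diuretic change are a sensible first response to isolated volume depletion in a heart failure population on loop diuretics. They do not address ketosis in someone who is acutely ill and taking a drug with a known DKA risk.

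For that second participant, the section that governs interruption of trial drug puts the pause after other measures. The participant's own advice, if it follows STOP-DKA, puts the pause first. A participant could hold a card saying stop while the site works from a rule saying try other steps first, and no cross-reference tells the site how to reconcile them.

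What is at stake is participant safety in a narrow case: continued dosing, within the wording of the rule, during an event that the protocol itself lists as a DKA precipitant. Section 2.1 reports adjudicated DKA of 2.7% on sotagliflozin 200 mg against 0.5% on placebo in earlier trials in type 1 diabetes, nearly all of it leading to hospital admission. That is why clear interruption wording is worth having here.

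**Working it through.** No formula applies. The check is to take each situation that the second bullet of 7.11.2 could cover and compare the order of steps in each text.

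**1. Ketones above 1.5 mmol/L, any cause.** The first bullet of 7.11.2 stops the drug. The STOP-DKA advice also stops it in a symptomatic participant. No conflict.

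**2. Vomiting, or symptoms pointing to DKA, with ketones at or below 1.5 mmol/L or not yet measured.**

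| Source | First step | Then |
|---|---|---|
| 7.11.2, second bullet | Fluids or loop diuretic adjustment, as appropriate | Cessation may be needed |
| Appendix 6, sick-day list (cited in Appendix 1) | Stop the drug | Ketone and glucose check, supplemental insulin and carbohydrate, hydration |
| Appendix 6, wallet card | Stop the drug | Ketone and glucose tests every 2 to 4 hours, fluid and carbohydrate, supplemental insulin |
| 7.8 | Check ketones, follow sick day rules as discussed locally | Participant has been taught when to discontinue and whom to contact |

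The order in 7.11.2 is the reverse of both Appendix 6 items. Section 7.8 presupposes that there is an answer to when therapy should stop in these events. Below the ketone threshold, the temporary-discontinuation section gives only a conditional one.

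**3. Investigator-judged volume depletion without vomiting or DKA symptoms.** 7.11.2 gives fluids or diuretic adjustment first. The Appendix 6 list is headed as principles for symptomatic individuals and is aimed at ketosis, so it does not clearly govern this case. No real conflict, and the existing order is defensible.

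**4. Other intercurrent illness without those features.** 7.11.2 leaves the decision to the investigator. Again Appendix 6 does not clearly speak to it.

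The mismatch is therefore confined to situation 2. It is not a remote case: by section 2.1, diarrhoea or vomiting is the usual setting for volume depletion, so the Appendix 1 row and the 7.11.2 bullet will often meet in the same participant.

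**The case against.** The case on the other side is substantial, and much of it stands.

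- **Stopping is already addressed.** Section 7.8 requires education on when to discontinue in these events, plus a contact route, and the schedule in Appendix 4 repeats glucose and ketone education from Visit 2 to Visit 8. This stands. A reader might infer that the protocol leaves the acutely ill participant without stopping advice; it does not. What remains is that 7.11.2 does not carry that advice through.
- **Investigators are free to stop at once.** The phrase about initial steps is qualified by appropriateness. This stands. A reader might infer that 7.11.2 requires dosing to continue; it does not.
- **Appendix 6 is not mandatory and local guidelines may replace it.** This stands, so the documents do not support reading this as a breach of a binding rule. It does not remove the point: Appendix 1 cites the STOP-DKA rules without qualification as the volume-depletion mitigation, and 7.8 gives the wallet card as an example of the alerts that all participants receive.
- **The lead-in.** The list opens "The trial drug will be temporary discontinued in the following circumstances", and a reader might take this as a contradiction with the permissive second bullet. That is loose drafting. The last bullet, on notifying the investigator after more than 5 days off drug, is not a stopping circumstance at all, and section 9.2 also treats cessation for illness as conditional. Nothing here rests on the lead-in.
- **A mandatory stop for any intercurrent illness would be too broad.** This stands. It would have no severity threshold, and it would remove discretion in situations 3 and 4, where discretion is reasonable.
- **Outside guidance.** Section 7.8 also directs management by external position statements that cannot be seen here. They may contain a stopping rule that settles the matter in practice.

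**Conclusion.** The point holds as a minor safety-wording inconsistency. For a participant who is vomiting or has symptoms suggesting DKA, with ketones at or below 1.5 mmol/L, the order of steps in 7.11.2 runs opposite to the sick-day advice cited in Appendix 1 and to the wallet card, and does not reflect the discontinuation education in 7.8.

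Its size cannot be given. The protocol states no rate of intercurrent illness. A reader might try to use the 2% for volume depletion in section 2.1, but that counts volume depletion of any kind, not ill participants kept on drug below the ketone threshold. Nor can an excess of DKA events be computed.

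A reader might also infer bias in the DKA comparison or in the KCCQ analysis, or a loss of power. The documents support none of these: the rule applies in both blinded arms, and nothing in the sample size or the primary analysis depends on it.

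The conclusion assumes that some sites use the STOP-DKA material or similar stop-first advice. Where local guidelines differ, the mismatch may be smaller or absent.

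**What to change.** Split the second bullet of 7.11.2.

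- **(a)** Vomiting, diarrhoea with inability to maintain fluid intake, or symptoms suggestive of DKA: pause trial drug and check ketones. Restart under the guidance already in the section (ketones below 0.6 mmol/L, symptoms resolved, investigator confirmation after more than 5 consecutive days off drug).
- **(b)** Other intercurrent illness, or investigator-judged volume depletion without the features in (a): investigator discretion, with fluids or loop diuretic adjustment first, as now.

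Keep the separate stop at ketones above 1.5 mmol/L. Cross-refer section 7.8 and the Appendix 1 volume-depletion row to this rule, and check that the participant card or local sick-day advice agrees with it.

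The cost is one amended bullet, two cross-references and a check of participant materials. The downside is a few more short drug interruptions in both arms, each recorded as an adverse event under 9.2.
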